6.1.3 Informed Consent – See Section 8.1.1

6.2 Safety and Other Assessments

Study procedures are specified in the SOA (Table 3). A study clinician, licensed to make medical diagnoses as the participating clinical site PI or appropriate sub-investigator, will be responsible for all study-related medical decisions.

- Medical history:
 - A complete medical history will be obtained by interview of subjects at the screening visit. Subjects will be queried regarding a history of significant medical disorders of the head, ears, eyes, nose, throat, mouth, cardiovascular system, lungs, gastrointestinal tract, liver, pancreas, kidney, urologic system, nervous system, blood, lymph nodes, endocrine system, musculoskeletal system, skin, and genital/reproductive tract. A history of any allergies, cancer, immunodeficiency, psychiatric illness, substance abuse, and autoimmune disease will be solicited.
 - At all subsequent visits an interim medical history will be obtained by interview of subjects and any changes since the previous clinic visit will be noted. The interim medical history should include an assessment for new medical conditions and symptoms suggestive of an AE.
- Physical examination:
 - A full physical examination will be performed at the screening visit and a symptom-directed (targeted) physical examination will be performed if indicated at all other timepoints specified in the SOA.
 - A full physical examination will include assessments of the following organs and organ systems: skin, HEENT, neck, lungs, heart, liver, spleen, abdomen, extremities, lymph nodes (axillary and cervical), and nervous system.

- Height and weight will be measured, and BMI calculated, at the screening visit only.
- Note presence of signs or symptoms consistent with solicited AEs to establish a baseline for subsequent assessment purposes (see **Sec 6.2.2**).
- A symptom-directed (targeted) physical examination will be performed if indicated at all other timepoints specified in the SOA.
 - Targeted physical examinations should also include an assessment for signs and symptoms suggestive of AEs. Interim or unscheduled physical examinations will be performed at the discretion of the participating clinical site PI or appropriate sub-investigator, if necessary, to evaluate AEs or abnormal clinical laboratory test results.
 - Reactogenicity assessments will include an assessment of illumination site reactions – erythema, edema/induration, pain and difficulty swallowing, as well as systemic reactions—fever, chills, headache, and nausea. Pre-illumination reactogenicity assessments will be performed immediately prior to first RD19 use to establish a baseline, then the use of the RD19 device will occur.
- Subjects will be observed in the clinic for at least 60 minutes post each RD19 illumination. The illumination site will be examined, post-use reactogenicity assessments will be performed, and any AEs/SAEs will be recorded on the appropriate e-CRF prior to discharge from the clinic. The oropharynx and surrounding tissues will also be examined on Days 1, 7, 14 and during unscheduled visits and early termination visits.
- Vital signs:
- Vital sign measurements will include systolic and diastolic BP, HR, and oral temperature. Vital signs will be measured at timepoints specified in the SOA. On Days 1, 7 and 14, vital sign measurements will be collected prior to device administration. Vital signs assessed on Day 1 prior to the first use of RD19 will be considered as baseline. Subjects must not eat or drink anything hot or cold within 10 minutes prior to taking their oral temperature or using the RD19 device.
- Clinical laboratory evaluations:
 - Fasting is not required before collection of clinical laboratory evaluations.
 - Urine pregnancy test will be performed locally by the site laboratory at the screening visit and at the final study visit. Results must be confirmed as negative prior to randomization on Day 1 and allocation and use of the RD19 device.
 - Clinical screening laboratory evaluations (CMP and CBC (diff) will be performed locally by the site laboratory).
 - Clinical safety laboratory evaluations will be performed locally by the site laboratory.
 - Methemoglobin will be measured prior to use of the device in the clinic and just prior to discharge from the clinic after 1 hour.
 - Blood and urine will be collected at timepoints specified in the SOA.

○ Diary Cards:

- All subjects will complete a Diary Card daily for the entire term of the study. Diary Cards will be reviewed with the subjects for any AEs (solicited injection site and systemic reactions, as well as unsolicited AEs), SAEs and concomitant medications. Diary Cards will be collected at the end of a volunteer's participation in the study.

○ Acceptability Assessment:

- All subjects will complete a brief survey of device tolerability and acceptability. This will be completed during the 60 minute follow-up period after device use in the clinic.

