| Physical Examination | X | *Targeted only | *Targeted only | *Targeted only |
| BMI | X | | | |
| Vital Signs | X | X | X | X |
| Methemoglobin | X | *Before and 60 minutes after device use | *Before and 60 minutes after device use | *Before and 60 minutes after device use |
| Lab Sample Collection & Processing | X | | | X |
| CBC and differential | X | | | X |
| CMP | X | | | X |
| Urinalysis | X | | | X |
| Urine Pregnancy Test | X | | | X |
| Concomitant Medication History/New | X | X | X | X |
| Device Illumination | | X | X | X |
| Acceptability Assessment of Device | | X | X | X |
| Distribution and train diary card | | X | | |

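### No blood pressure or heart rate reading is scheduled after illumination, so an acute, transient, symptom-free haemodynamic change is not measured in a study of acute safety

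*Combined protocol and SAP*

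**What the plan says.** Section 6.2 defines the measurements: "Vital sign measurements will include systolic and diastolic BP, HR, and oral temperature". It fixes their timing at the treatment visits: "On Days 1, 7 and 14, vital sign measurements will be collected prior to device administration". It also sets the reference point: "Vital signs assessed on Day 1 prior to the first use of RD19 will be considered as baseline".

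Table 3 in Section 1.2 agrees. The vital-signs row reads "Vital Signs | X | X | X | X", one mark per visit with no before/after split. The methemoglobin row in the same table carries, for Days 1, 7 and 14, the note "Before and 60 minutes after device use".

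After use, Section 6.2 keeps the subject on site: "Subjects will be observed in the clinic for at least 60 minutes post each RD19 illumination". The tasks for that period are stated: "The illumination site will be examined, post-use reactogenicity assessments will be performed, and any AEs/SAEs will be recorded". The second methemoglobin reading and the acceptability survey also fall in this period. Reactogenicity covers local reactions "as well as systemic reactions—fever, chills, headache, and nausea". BP and HR are not among the post-use tasks.

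Section 7.4.1 plans summaries of solicited and unsolicited adverse events, serious adverse events and laboratory data. It describes no summary of vital signs.

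**The concern.** This is a first-in-man study, and Section 3.2 names acute safety as its primary objective. Sections 1.1 and 2.1 describe a device that releases bound nitric oxide instantaneously. The protocol already allows for a systemic consequence: it brackets device use with methemoglobin readings, and Section 4.2 excludes people with a history of hypersensitivity or severe allergic reaction to nitrates or nitrites. BP and HR are inexpensive systemic readings, but they are scheduled only on the pre-use side of each illumination.

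The gap reaches the primary endpoint, which is the frequency, grade and attribution of adverse events. Section 6.1.2 lists vital signs among the physiologic parameters and treats every abnormal clinical finding after device use as an adverse event. A symptom-free abnormal reading that is never taken cannot be counted, graded or attributed, and cannot contribute to the Grade 3 criterion among the pausing rules in Section 5.5.1. For BP and HR, a clean acute-safety result would partly reflect the absence of measurement.

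**Working it through.** **Inputs.** Timing of vital signs: Section 6.2 and Table 3. Timing of methemoglobin: Table 3 and Section 6.2. Subjects: 25 (Section 4). Treatment visits: Days 1, 7 and 14. SD of within-subject change in systolic BP: not given in the documents; 8 to 10 mmHg is assumed. The plan gives no figure of its own on this point to reproduce.

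**Step 1: count the scheduled readings per subject on treatment days.**

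| Measurement | Before use | After use, same visit | Within-visit pairs |
|---|---|---|---|
| BP, HR, oral temperature | 3 | 0 | 0 |
| Methemoglobin | 3 | 3 | 3 |

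**Step 2: set each kind of change against what could reveal it.**

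- *Sustained or cumulative change in BP or HR.* The Day 7 and Day 14 pre-use readings follow days of twice-daily use and can be compared with the Day 1 pre-use baseline. That gives 2 comparisons per subject, so this is detectable.
- *Symptomatic change.* The observation period, adverse event recording, and targeted or unscheduled examinations (Section 6.2) can pick this up.
- *Fever.* It is part of the post-use reactogenicity assessment and a solicited event on the daily diary (Section 6.2.2), so it is detectable. The supplied text does not say how temperature is taken at that point, and a rise short of fever could be missed.
- *Transient, symptom-free change in BP or HR after illumination.* A pre-use reading cannot show the response to the illumination that follows it. The solicited list has no haemodynamic item, and the additional examinations are made if indicated or if necessary. No scheduled procedure measures this change.

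**Step 3: what the added readings would give.** One post-use set at each visit gives up to 25 × 3 = 75 within-visit pairs. These are three repeated measures on 25 subjects, not 75 independent pairs, so precision is stated for one visit:

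Half-width of the 95% CI = t(0.975, 24) × SD / √25 = 2.064 × SD / 5

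- SD 8 mmHg: 2.064 × 8 / 5 = 3.3 mmHg
- SD 10 mmHg: 2.064 × 10 / 5 = 4.1 mmHg

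**The case against.** **No endpoint or planned estimate depends on it.** The endpoints are adverse events and serious adverse events. Section 7.4.1 plans no vital-sign analysis, Section 2.2.1 lists no haemodynamic risk, the documents place the nitric oxide effect in epithelial tissue with light penetration below 0.5 mm, and the sponsor rates the device as not significant risk. It stands that no planned estimate is invalidated and that a systemic effect is only an inference. The omission still matters, because abnormal post-use findings are adverse events by the plan's own rule and the protocol already tests for one systemic effect around each in-clinic use.

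**The plan can detect change in other ways.** A reader might infer that no post-use change in BP, HR or temperature could be detected at all. The documents do not support that: fever, symptomatic change and sustained change are each covered. Nor do they show that every subject leaves without a repeat reading, since unscheduled examinations are allowed. They show only that none is scheduled.

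**A reading at 60 minutes may miss an immediate effect.** This stands. The documents give no time course for any BP or HR effect, so a single late reading could reassure falsely. An additional early reading is therefore preferable.

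**The added data would be weak evidence of a device effect.** This also stands. The study is single-arm and open-label, and an hour in clinic may itself move BP and HR. It would also be too strong to say that a mean change of 5 mmHg could be seen or excluded. With 25 subjects and a true mean change of 5 mmHg, the chance that the 95% CI excludes zero is about 85% at SD 8 and 67% at SD 10. Neither the 5 mmHg nor the SD comes from the documents.

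**Conclusion.** The point holds in a limited form. No BP or HR reading is scheduled after illumination at any visit, so an acute, transient, symptom-free haemodynamic change is not measured and cannot enter the adverse event counts. Per subject there are 3 pre-use sets, 0 scheduled post-use sets and 0 within-visit pairs, against 3 pairs for methemoglobin. This conclusion rests on the schedule alone and needs no assumption about effect size. Only the precision of about 3.3 to 4.1 mmHg for mean systolic change at one visit depends on the assumed SD of 8 to 10 mmHg and on all 25 subjects contributing a pair.

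The plan is not internally contradictory here and its planned analyses are unaffected. It is a gap in measurement that should be closed, because doing so is cheap and bears on the study's stated primary objective.

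**What to change.** 1. In Section 6.2 and the vital-signs row of Table 3, change the entries for Days 1, 7 and 14 to readings before and after device use, within the existing observation period. Take one post-use set alongside the second methemoglobin reading and, because the proposed effect is immediate, preferably another shortly after illumination. State the reason for the chosen times.
2. In Section 7.4.1, add a descriptive summary of within-subject post-minus-pre change in each vital sign, by visit and post-use time, with a 95% CI. State that, without a control arm, the change mixes any device effect with settling during the clinic stay.

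The cost is a few minutes of existing staff time per visit and extra e-CRF fields. No added visit, blood sample or longer clinic stay is needed.

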1. PROTOCOL SUMMARY

1.1 Executive Synopsis

Rationale for Proposed Clinical Study

In December 2019 the Wuhan Municipal Health Committee identified an outbreak of viral pneumonia cases of unknown cause. Coronavirus ribonucleic acid (RNA) was quickly identified in some of these patients. As of July, 2020 there were 15.5 million confirmed cases (>4 million in the US) and over 600,000 deaths (~145,000 in the US). There are currently no FDA approved prophylactic interventions against SARS-CoV-2 while social distancing and personal protective equipment constitute our only viable countermeasures to help reduce the incidence of community transmission. While vaccine candidates are being developed at unprecedented speeds, their efficacy is completely unknown and will not be known for many months.

Therefore, there is an urgent public health need for rapid development of novel protective measures, as well as improved therapeutic interventions. The EmitBio™ RD19 device emits visible blue light to stimulate host defenses (as explained below) to eliminate invading pathogens in the oropharynx and surrounding tissues. The RD19 device does this without additional photosensitizers or chemical reagents that are typically employed with traditional photodynamic therapeutics. Specifically, selected wavelengths of light have been evaluated across the visible spectrum, and it was discovered that safe, visible blue light emitted from non-coherent LED sources could perform both of the following functions:

- (1) upregulate the sustained production of nitric oxide in epithelial tissue through increase of nitric oxide synthases (NOSs);

- (2) stimulate the instantaneous release of the body's bound stores of nitric oxide.

Nitric oxide produced naturally in epithelial tissues also induces and recruits effector cells of the innate immune system, including natural killer (NK) cells, neutrophils and macrophages to phagocytize virus-infected cells at the site of primary infection.

1.1.1 Claims and Indication:

The EmitBio™ RD19 device uses blue light to boost the body's natural immune response, which when combined with social distancing and proper mask use as part of healthy living, may help to reduce the risk of infection by respiratory viruses like influenza and SARS-CoV-2.

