6. STUDY ASSESSMENTS AND PROCEDURES

6.1 Screening Assessments

6.1.1 Screening Procedures

There is a small amount of risk to subjects who report that they are in good health but have an unknown health problem at the time of screening. At the screening visit, and prior to any other study-related activities, the participating clinical site PI or appropriate sub-investigator will provide the subject with detailed study information and will obtain written informed consent.

Some or all of the following assessments are performed during the screening visit to determine eligibility requirements as specified in the inclusion and exclusion criteria:

- Obtain medical history focusing on conditions per protocol exclusion criteria.
- Review pre-study medications and therapies up to 10 days prior to the start of screening that could impact the use of, or response to, the device and record on the appropriate e-CRF.
- Measure vital signs (HR, BP, and oral temperature) and height and weight for determination of BMI.
- Perform full physical examination which will include assessments of the following organs and organ systems: skin, head, ears, eyes, nose, and throat (HEENT), neck, lungs, heart, liver, spleen, abdomen, extremities, lymph nodes (axillary and cervical), and nervous system.
- Obtain blood and urine for clinical screening laboratory evaluations:
 - Hematology
 - CBC with differential
 - Methemoglobin level (Pulse Ox method)
 - CMP (fasting or non-fasting)
 - Urine pregnancy test (in women of childbearing potential)
- Review inclusion and exclusion criteria.

Clinical screening laboratory evaluations will be performed locally by the site laboratory.

The overall eligibility of the subject to participate in the study will be assessed once all screening values are available. The screening process can be suspended prior to complete assessment at any time if exclusions are identified by the study team.

Study subjects who qualify for inclusion will be scheduled for enrollment and their day 1 visit.

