7.4 Statistical Analyses

7.4.1 Primary Safety Analyses

Summaries and analyses of safety data will be presented for the Safety Analysis Population.

Solicited AEs will be summarized overall and by maximum severity post through study day 7, post study period days 7 -14 and overall. Additionally, solicited AEs will be analyzed by taking the most severe response (grouped as either modified per protocol or per protocol), dichotomizing into a binary variable (none versus mild, moderate, or severe) and using standard techniques, such as exact confidence intervals (CI), to summarize the proportion of subjects reporting each solicited sign or symptom.

Unsolicited non-serious AEs will be collected from the time of first device use through study day 14. Unsolicited AEs will be coded by MedDRA™ for preferred term and system organ class (SOC). All SAEs will be collected from the time of first device use through the study day 14. The number of SAEs will be reported by detailed listings showing the event description, MedDRA™ preferred term and SOC, study day of occurrence, severity, relatedness, and outcome for each event. Non-serious unsolicited AEs will be summarized as number and percentage of subjects reporting at least one event in each MedDRA□ preferred term and SOC, cross tabulated by severity and relationship to the study device. Additionally, the proportion of subjects and exact 95% CIs of AEs in aggregate and by MedDRA□ categories will be computed.

Clinical laboratory data, including methemoglobin measurements, will be summarized by severity and as the maximum numeric value over the entire study. Graphical presentations may include box plots and shift plots.

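### Section 7.4.1 reduces methemoglobin to a study-wide maximum that may be a pre-use value, so the planned summary does not isolate an acute effect of device use

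*Combined protocol and SAP*

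**What the plan says.** **Readings.** The Schedule of Activities (Section 1.2, Table 3) has methemoglobin at screening and, on Days 1, 7 and 14, "Before and 60 minutes after device use". Section 6.2 describes the same pair: one reading before the device is used in the clinic and one "just prior to discharge from the clinic after 1 hour". Section 6.2 also says: "Subjects will be observed in the clinic for at least 60 minutes post each RD19 illumination". Pulse oximetry is named as the method in the screening list of Section 6.1.1; the post-use text in Section 6.2 names no method.

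**Analysis.** Section 7.4.1 summarises clinical laboratory data, methemoglobin included, by severity and "as the maximum numeric value over the entire study". It defines no change from the pre-use reading and does not say whether screening and pre-use readings enter the maximum. Box plots and shift plots are mentioned as possibilities only. Section 7.4.3 adds a summary of baseline laboratory values but does not say which methemoglobin reading is the baseline.

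**Role in the study.** Section 3.1 names methemoglobinemia as the hematological safety assessment at every visit. Section 3.2 makes acute safety the primary objective.

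**The concern.** Methemoglobin is the only laboratory-type measure that the plan times to a device use. The blood count, metabolic panel and urinalysis are taken at screening and Day 14, and Section 6.2 takes vital signs on use days before the device is used. The pre-use and post-use pairs are therefore the study's direct objective evidence on what happens in the hour after illumination.

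The planned numeric summary discards the pairing. A maximum over all readings mixes values taken before and after use, so it can miss an effect or suggest one. It misses an effect when a high pre-use value sets the maximum and rises at other visits stay below it. It suggests one when it is compared with the screening value: if screening is among the readings, the maximum cannot lie below it, so the comparison can show only no change or a rise. In both cases a reader of the report could not tell whether methemoglobin moved after use.

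**Working it through.** **1. Count the readings** (Table 3 and Section 6.2; 25 subjects from Section 4).
- Per subject: 1 at screening + 3 visits × 2 = 7.
- Post-use: 3. Not post-use: 1 + 3 = 4.
- Study maximum: 7 × 25 = 175 readings, of which 3 × 25 = 75 are post-use. This gives up to 75 same-day pairs.

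**2. What the maximum measures.** Let S be screening, P the pre-use reading and A the post-use reading on a given day.
- Planned summary: M = max(S, P1, A1, P7, A7, P14, A14).
- Acute change on day d: D_d = A_d − P_d.
- If a P or S is largest, M contains no post-use value. If A_d is largest, M = A_d, and D_d still cannot be recovered without P_d.

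**3. How often M is not a post-use value.** If the readings are exchangeable (no device effect, no trend over visits, ties ignored), each is equally likely to be the largest. The answer depends on which readings count, which 7.4.1 leaves open:

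| Readings counted | Not post-use / total | Probability |
|---|---|---|
| All seven | 4/7 | 57% |
| Screening excluded | 3/6 | 50% |
| Screening and Day 1 pre-use excluded | 2/5 | 40% |
| Post-use only | 0/3 | 0% |

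A real rise after use would lower the first three figures. They describe the no-effect case.

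**4. What the pairs offer.** If all 25 subjects give a pair at a visit, the 95% confidence interval for the mean change has half-width 2.064 × SD/√25 = 0.41 SD, where SD is that of the changes and 2.064 is the t quantile on 24 degrees of freedom. The documents give no SD, so this cannot be put in methemoglobin units.

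**5. What one reading at about 60 minutes can say about a peak.** The documents give no time to peak and no clearance rate. All kinetics here are assumptions, used only to show the range.
- First-order decline from a peak at t_p, half-life h: share left at 60 minutes = 0.5^((60 − t_p)/h). With t_p = 5 minutes: 8% at h = 15 minutes, 53% at 60 minutes, 81% at 180 minutes.
- Formation and clearance, f(t) ∝ e^(−kt) − e^(−at), with a and k equal to ln 2 divided by the formation and clearance half-lives:
  - Formation 5, clearance 15 minutes: peak at 12 minutes, 16% left at 60.
  - Formation 20, clearance 60 to 180 minutes: peak at 48 to 71 minutes, and the reading is 97% to 100% of it.
  - Formation 30, clearance 180 minutes: peak at 93 minutes, after the reading, which is at 93% of it.

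One post-use reading cannot tell these cases apart.

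**6. Reading time.** Table 3 fixes 60 minutes. Section 6.2 ties the reading to discharge, after an observation of at least 60 minutes, so actual times may run later and may vary between subjects.

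**The case against.** **The highest value is a proper safety summary.** In a descriptive first-in-man study the worst level a subject reached matters whenever it occurred. Pre-use readings on Days 7 and 14 are also not exposure-free, because they follow days of home use; a rise that builds up over the study could appear there and would be lost in a same-day change. This stands. It is a reason to keep the overall maximum as an additional summary and to show pre-use values by visit, not to leave out the paired change.

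**Other safeguards exist.** Section 6.1.2 treats abnormal laboratory values after device use as adverse events, and methemoglobin is also summarised by severity. This stands in part: clear abnormalities should surface. A shift within the normal range would not. The Appendix 2 grading tables are not in the text I have, so I cannot say how methemoglobin is graded.

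**The pairs are collected and can be analysed anyway.** True, and 7.4.1 allows optional shift plots. But the choice of baseline and contrast would then be made after open-label data had been seen.

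**A stronger reading is tempting.** The synopsis says the light can "stimulate the instantaneous release of the body's bound stores of nitric oxide". A reader might infer that methemoglobin peaks within minutes, that the 60-minute reading misses the peak, and that the rise is understated by 21% to 50%. That range comes from 1 − 2^(−1/h) with h = 3 and 1 hours, and it assumes a peak at time zero. The documents do not support this. They describe fast release of nitric oxide, not the course of methemoglobin, which lies downstream and for which they give no kinetics. The same sentence also claims sustained production. Step 5 shows that a peak near or after 60 minutes is equally open. Nor does the plan call its maximum a peak.

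**Conclusion.** The point holds as a gap in the analysis text. The only numeric methemoglobin summary stated in 7.4.1 does not isolate an acute effect of device use, because four of the seven scheduled readings per subject are not post-use. Under exchangeability the maximum is one of those four with probability 57%; under narrower readings of which values count, 50% or 40%. That the maximum does not give the change across a use needs no such assumption.

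The size is minor. The primary endpoints are adverse event frequency, grade and attribution, the study tests no hypothesis, and the needed data are already scheduled. A single reading at about 60 minutes, for which no reason is given, cannot locate or bound a peak. That is a limit to state, not evidence that a peak is missed.

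**What to change.** 1. **Section 7.4.1, change.** For each of Days 1, 7 and 14, summarise the change from the same-day pre-use reading to the 60-minute post-use reading (number of pairs, mean with 95% confidence interval, median, range), and list individual values. Show the pre-use values by visit alongside.
2. **Section 7.4.1, maximum.** Report the maximum over post-use readings only. If the maximum over all readings is kept, label it as such and say which readings it includes.
3. **Table 3 and Section 6.2.** Reconcile the two descriptions of the reading time, and record the actual time of each reading and of the end of illumination.
4. **Limitation.** State that one reading at about 60 minutes cannot locate or bound a peak, and give the reason for choosing that time if there is one.

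Items 1 and 2 cost a few lines of text and some programming; item 3 costs time fields on the e-CRF if they are not already there; item 4 costs a sentence or two. No visit or reading is added.

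An extra reading early in the observation hour is optional. It would help describe the time course, and it would probably need no blood draw if the screening method (pulse oximetry) also applies on Days 1, 7 and 14, which the documents imply but do not state. It would not by itself establish a peak, and the point above does not depend on it.
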